2.0 OBJECTIVES AND SCIENTIFIC AIMS

Hypothesis: Targeting the MAPK pathway and FGFR signaling by combining BGJ398 and imatinib will be a safe and a more effective therapeutic strategy than imatinib alone in patients with untreated locally advanced or metastatic GIST.

Primary Objective:

Phase Ib study: to assess the safety and tolerability of treatment with BGJ398 (an FGFR inhibitor) in combination with imatinib and to determine the MTD and the recommended Phase II dose (RP2D) and schedule of the combination therapy in locally advanced or metastatic GIST patients.

Phase II study: to assess the efficacy (RR = complete response (CR) + partial response (PR)) at 32 weeks of the combination therapy of BGJ398 and imatinib in patients with untreated locally advanced or metastatic GIST, using RECIST 1.1.

Secondary Objectives:

Phase Ib study: to assess the pharmacokinetics of BGJ398 and imatinib; to estimate RR (CR + PR) by 32 weeks by both RECIST 1.1 and CHOI criteria, progression free survival (PFS) and clinical benefit rate (CR+PR+SD) at 32 weeks of the combination therapy of BGJ398 and imatinib in all locally advanced or metastatic GIST patients who have received prior therapy with imatinib.

Phase II study: to assess the RR (CR + PR) of the combination therapy of BGJ398 and imatinib by CHOI criteria, and by EORTC criteria for partial response on FDG PET (25% reduction in PET SUVmax), PFS, overall survival (OS), clinical benefit rate (CR+PR+SD) at 32 weeks and resectability rates in patients with untreated locally advanced or metastatic untreated GIST.

Correlative Objective:

We will analyze the molecular and signaling effects of imatinib in combination with BGJ398 using tumor biopsy specimens collected pre- and post-treatment (C1D8), and (if feasible) upon disease progression. Biopsies will be performed on a minimum of 20 patients from the Phase II portion of the study across all sites. In addition, blood and serum will be collected throughout the trial. All of these samples will be used to analyze the pharmacodynamic effects of BGJ398 in combination with imatinib on the following and correlate with clinical response to help identify promising prognostic or predictive biomarkers for further study:

- ETV1 protein level by western blot (WB)
- ETV1-dependent transcriptome (expression profile of *ETV1*-dependent gene targets) by nanostring.

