6.0 CRITERIA FOR SUBJECT ELIGIBILITY

6.1 Subject Inclusion Criteria

Patients eligible for inclusion in this study have to meet **all** of the following criteria:

Inclusion criteria:

- Patients must have pathologically confirmed GIST.
- In the Phase Ib portion, must have locally advanced or metastatic GIST and have progressed on imatinib.
- In the Phase II portion, patients must be newly diagnosed or imatinib treatment naïve in the advanced/metastatic setting. Prior adjuvant imatinib therapy is allowed as long as disease

MEMORIAL SLOAN-KETTERING CANCER CENTER IRB PROTOCOL

IRB#: 14-140 A (7)

recurrence was documented ≥ 90 days after last dose of imatinib and imatinib has not yet been restarted.

- Patients must be at least 18 years of age.
- Disease must be measurable by RECIST 1.1.
- ECOG Performance Status 0 or 1.
- Adequate renal, hepatic, and hematologic function as the following: Serum Creatinine ≤ 1.5 mg/dL, Total Serum Bilirubin ≤ 1.5 x upper limit of normal (ULN) unless due to Gilbert's Disease, Serum AST (SGOT) and/or ALT (SGPT) ≤ 2.5 x ULN (or ≤ 5.0 x ULN if considered due to tumor), ANC $\geq 1500/\text{mm}^3$, Platelets $\geq 100,000/\text{mm}^3$, and hemoglobin $\geq 10\text{g/dL}$.
- Patients of childbearing potential must have a negative blood pregnancy test within 14 days of treatment. Patients must agree to use a reliable barrier method of birth control during and for 3 months following the last dose of study drug.
- Patient must have adequate cardiac function (left ventricular ejection fraction (LVEF) $\geq 50\%$ as determined by a multigated acquisition (MUGA) scan or echocardiogram; and QTc interval ≤ 480 ms by Fridericia's formula (QTcF).
- Patient must be able to take oral medications.
- Patients must sign an informed consent document.

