13.0 CRITERIA FOR REMOVAL FROM STUDY

Patients will be removed from study when any of the criteria listed below applies. The reason for study removal and the date the patient was removed must be documented in the EDC system. Patients on the Phase II study may be replaced if they come off study for reasons other than progressive disease prior to receiving their first dose of BGJ398. Unless otherwise stated, patients will be included in the safety and/or efficacy analysis as described in Section 14.

A dose interruption of ≥ 28 days will require the patient to be discontinued from the study (with the exception of patients who undergo surgery). Local procedures (e.g. surgery, embolization) are permitted on this trial a) if clinically indicated or b) if response to therapy converts the patient into a surgical candidate. All drugs will be held for at least one week prior to the local procedure. Patients will resume therapy when deemed clinically safe, but no sooner than 1 week and no later than 5 weeks after the procedure. If a patient falls out of this window, consideration should be had for withdrawal from the study based on clinical reasons for the delay. Patients who have had a local procedure will be allowed to remain on the study if they have measurable disease (RECIST 1.1) after the procedure. Patients who are rendered disease free will be taken off the study and can be considered for adjuvant imatinib per standard of care. Conversion to resectability rate will be a secondary endpoint.

MEMORIAL SLOAN-KETTERING CANCER CENTER
IRB PROTOCOL

IRB#: 14-140 A (7)

Duration of Therapy: In the absence of treatment delays due to adverse events, treatment may continue until one of the following criteria applies:

- Disease progression,
- Intercurrent illness that prevents further administration of treatment,
- Unacceptable adverse event(s),
- Patient decides to withdraw from the study, or
- General or specific changes in the patient's condition render the patient unacceptable for further treatment in the judgment of the investigator.
- Inability of the patient to comply with the requirement of the protocol for treatment or evaluation.

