Response rate (RECIST 1.1) will be determined as the proportion of patients evaluable for efficacy (defined as patients who receive at least one dose of the combination regimen) who have complete response or partial response defined by the RECIST 1.1 with a one-sided 90% confidence interval (CI) provided. Patients missing post baseline assessment of response will be considered non-responders for the primary endpoint at that time point.

The steady state serum imatinib trough levels will be obtained and evaluated in the two-week imatinib lead in phase (two samples/patient) and in the combination therapy phase (2 samples/patient) from all patients in the Phase II portion of the trial. We will evaluate the effects of BGJ398 on imatinib steady state trough levels by comparing the values at these two time points (before and after lead in period). We will compare the ranges we obtain with the ranges reported by Demetri et al JCO 2009 and assess whether the effects are considered subtherapeutic, therapeutic, or

MEMORIAL SLOAN-KETTERING CANCER CENTER
IRB PROTOCOL

IRB#: 14-140 A (7)

supra-therapeutic. This analysis may inform future trials with this combination and will not change the dose that will be given in the combination regimen.

The secondary endpoints of the phase 2 portion include:

- (1) RR by CHOI criteria. It will be determined as the proportion of patients evaluable for efficacy who have complete response or partial response defined by the CHOI criteria with a two-sided 95% CI provided.
- (2) RR by EORTC criteria. It will be determined as the proportion of patients evaluable for efficacy who have complete response or partial response defined by the EORTC criteria with a two-sided 95% CI provided.
- (3) Progression free survival and Overall Survival. PFS and OS will be calculated using a Kaplan-Meier estimate among all patients enrolled. They are defined from the start of imatinib treatment, i.e. the lead in period is included in this endpoint. Patients on the Phase II portion who stop study prior to receiving a dose of BGJ398 for reasons unrelated to progression (e.g. intolerance to imatinib) will be censored at the time of withdrawal. Patients who have not had the event of interest by the end of the study will be censored at the time of last follow-up.
- (4) Resectability rate. It will be calculated by the proportion of Phase II patients who have completed 1 cycle of treatment who have resection of their disease with a two-sided 95% CI provided.

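### The resectability rate counts any resection among patients who completed one cycle, which is not the conversion rate named in Section 13 and is likely, though not certainly, too high

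*Combined protocol and SAP*

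**What the plan says.** Section 14.0, secondary endpoint (4), gives the only calculation rule: the share of patients in Phase II "who have completed 1 cycle of treatment who have resection of their disease", with a two-sided 95% confidence interval. The rule does not mention baseline status, response, or the reason for the operation.

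Section 13.0 states that local procedures such as surgery or embolization are "permitted on this trial a) if clinically indicated or b) if response to therapy converts the patient into a surgical candidate". The same paragraph ends: "Conversion to resectability rate will be a secondary endpoint". Section 2.0 lists only "resectability rates in patients with untreated locally advanced or metastatic untreated GIST", and the summary in Section 1.0 likewise speaks of resectability without conversion.

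The other Phase II endpoints use different sets. The RECIST, Choi and EORTC response rates use patients evaluable for efficacy, "defined as patients who receive at least one dose of the combination regimen". PFS and OS use all enrolled patients. A cycle is 28 days and cycle 1 begins with the first combination dose (Section 9.0), so only the resectability rate requires a patient to have come through those 28 days.

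On baseline status, Section 6.1 says that Phase II "patients must be newly diagnosed or imatinib treatment naïve in the advanced/metastatic setting". No criterion requires unresectable disease, and the Phase II calendar (Table 11) schedules no assessment of resectability.

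**The concern.** There are two separate difficulties. First, the denominator is conditioned on a post-baseline event. A patient who takes one combination dose and stops in cycle 1 counts as a non-responder under the missing-assessment rule for the primary endpoint, but drops out of the resectability rate altogether.

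Second, the numerator counts operations, while Section 13 names conversions. A patient who was operable at entry, or who was operated on for another clinical reason, scores as a success. A patient who becomes operable but has no surgery scores as a failure.

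Readers of a single-arm trial would take this rate as evidence that the combination makes tumours operable. With 44 patients, a few cases classified differently change the figure visibly.

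**Working it through.** **Base.** The plan gives no expected rate, precision or dropout for resectability, so there is no figure of its own to reproduce on this endpoint. The sample size it rests on does reproduce. With 44 patients and success at more than 24 responses (at least 25), the exact binomial gives a type I error of 0.0775 at 45% and power of 0.9011 at 65%, matching the stated 0.08 and 0.1 (type II). I take 44 as the full efficacy-evaluable denominator. All counts below are assumptions.

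**Denominator alone.** Let x be the number of resections, all among patients who completed cycle 1, and d the number who did not complete it. The planned rate is x/(44 − d), the reference is x/44, and their ratio is 44/(44 − d).

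| d | 44/(44 − d) | Planned rate at x = 6 | Reference |
|---|---|---|---|
| 2 | 1.048 | 6/42 = 14.3% | 6/44 = 13.6% |
| 4 | 1.100 | 6/40 = 15.0% | 13.6% |
| 6 | 1.158 | 6/38 = 15.8% | 13.6% |
| 8 | 1.222 | 6/36 = 16.7% | 13.6% |

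Exact 95% intervals are 5.2% to 27.4% for 6/44, 5.7% to 29.8% for 6/40 and 6.4% to 32.8% for 6/36. For x from 4 to 10 and d from 2 to 8, the shift runs from +0.4 points (4/42 − 4/44) to +5.1 points (10/36 − 10/44).

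The ratio holds only if none of the d patients is resected. If one of four is resected before finishing cycle 1, that patient leaves numerator and denominator alike, and the planned 6/40 = 15.0% lies below 7/44 = 15.9%.

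**Numerator and denominator together.** Let c be true conversions (all among completers), m resections that are not conversions, and u converted patients without surgery. The planned rate is (c − u + m)/(44 − d) and the target is c/44. With c = 6 and d = 4 the target is 13.6%, and each unit of m or u moves the planned rate by 1/40 = 2.5 points.

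| m | u | Planned rate | Difference from 13.6% |
|---|---|---|---|
| 0 | 0 | 6/40 = 15.0% | +1.4 points |
| 2 | 0 | 8/40 = 20.0% | +6.4 |
| 4 | 0 | 10/40 = 25.0% | +11.4 |
| 2 | 2 | 6/40 = 15.0% | +1.4 |
| 0 | 1 | 5/40 = 12.5% | −1.1 |
| 0 | 2 | 4/40 = 10.0% | −3.6 |

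Since 40 × 6/44 = 5.45, the planned rate is above target when m is at least u, and below it once u exceeds m by one.

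**The case against.** The strongest reply is that this is a transparent, prespecified descriptive rate, that requiring some exposure before judging surgical conversion is defensible, and that nothing is tested on it. That it is descriptive stands. The exposure argument does not explain why this endpoint alone uses such a set, and the plan gives no reason.

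Several stronger readings are tempting, and the documents do not support them:

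- *The rate is certainly biased upward.* Converted patients without surgery are missed, and early resections drop out, so the net direction is not fixed.
- *Section 13 defines the endpoint as surgery after conversion by response.* It names a conversion rate but gives no numerator and does not tie the rate to the second reason for surgery. The two reasons are not stated to be exclusive, and they also cover embolization, which is not resection.
- *Many early progressions are removed.* The first scheduled scan is at C3D1, after two cycles, so only unscheduled or clinical progression could remove a patient in cycle 1. Section 3.1.1 puts primary resistance on imatinib at about 5% within two months, or 0.05 × 44 = 2.2 patients, not all of them in the first cycle. Toxicity exits are possible, but no rate is given.
- *The response-rate denominator is free of such conditioning.* It also requires a patient to pass the two-week lead-in and receive BGJ398. The difference is one of degree.

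Background text, such as the imatinib-levels item in Section 10.2, describes the disease as inoperable, which would make most resections conversions. Eligibility does not enforce this, so the numerator problem remains, though its size is unknown.

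**Conclusion.** The point holds in limited form. Followed as written, Section 14 drops patients who stop in cycle 1 and scores any resection as a success, so it does not estimate the conversion rate that Section 13 names. Upward bias is likely but not certain.

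The denominator effect is modest: 5% to 22% relative for an assumed d of 2 to 8, and 1.4 points in the 6-resection, d = 4 case, well inside the confidence interval. The numerator mismatch can matter more, at 2.5 points per misclassified patient at d = 4. A reader might infer that the reported rate could be double the true one. For instance, if three of six resections were not conversions, 6/40 = 15.0% would stand against 3/44 = 6.8%. That result comes almost entirely from the assumed split, for which the documents offer no basis.

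No hypothesis test or decision rule uses this rate. The rule of more than 24 responses in 44 and the primary conclusion are untouched.

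**What to change.** In Section 14, take all efficacy-evaluable Phase II patients (at least one combination dose) as the denominator, as for the response rate. Use one endpoint definition in Sections 2, 13 and 14. Report resections that followed conversion by response as the conversion rate, and list all other resections separately with their reason. State that converted patients who had no surgery are not captured by this count.

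The denominator and the aligned definition cost only wording. Separating the resections may need a data field for the reason for surgery, and one for baseline resectability would help. Section 13 distinguishes the reasons when permitting procedures, but the documents do not show that either item is recorded. The reported figure may be slightly less favourable. No treatment or surgical rule changes.

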For the purpose of exploratory studies, the phase 2 portion includes the phenotypic (by IHC), genetic, transcriptomic, epigenetic, and pharmacodynamic characterization of the tumors as correlative endpoints. Twenty patients are planned to have mandatory paired biopsies (pre and post treatment), and the remaining patients will provide optional biopsies if funding is identified. This sample size provides 80% power to detect a standardized difference of 0.55 assuming 2 sided one sample paired t test at 10% significance level. The variable of interest will be change in protein levels.

The analysis of the exploratory studies is planned as follows.

- 1) ETV1 protein level by western blot (WB) as a continuous variable. The change of ETV1 protein level (before vs. after the combination therapy) will be recorded as up, down, and no-change (categorical response). It will be tabulated with the percentages provided. It will be correlated with response using the Fisher's exact test.
- 2) ETV1-dependent transcriptome (expression profile of ETV1-dependent gene targets) by nanostring. The expression change of ETV1 target genes (before vs. after the combination therapy) will be correlated with clinical response using the Wilcoxon rank test. The outcome will be a composite score (based on gene expression level and directionality of the changes), and it is continuous variable.
- 3) Cell proliferation (Ki-67) and apoptosis (cleaved caspase-3) by IHC. Descriptive statistics will be provided. These variables are continuous.
- 4) MAP kinase pathway and other pathways downstream of KIT and FGF signaling using standard antibodies (phospho-ERK, phospho-KIT, phospho-MEK, phospho-AKT, etc) by IHC. Descriptive statistics will be provided.
- 5) KIT/PDGFRα mutational status in matched tumor biopsy specimens collected prior to therapy, after combination therapy and upon disease progression. FGFR and FGF2 expression on tumor

MEMORIAL SLOAN-KETTERING CANCER CENTER IRB PROTOCOL

IRB#: 14-140 A (7)

samples by IHC analyzed as a binary covariate and FGF2 ligand levels in collected serum by ELISA analyzed as a continuous covariate.

- 6) Protein expression of FGF2, sVEGFR1, sVEGFR2, VEGF-A, -C, -D, cKIT, PLGF, and Tie2 in tumor tissues utilizing commercially available immunoassay kits. This will be a continuous variable.

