- 7) Expression of genes implicated in GIST pathogenesis and signaling, including KIT, ETV1, FGFR1, -2, -3, and -4; DUSP6, SPRY2, and SPRY4 will be analyzed as a continuous covariate. Changes before and after treatment will be assessed and correlated with clinical response.

In most of the above studies, we are interested in looking at changes in expression levels, protein measurements, or mutation status before and after treatment. The correlative endpoints described above will be correlated with response (binary outcome defined as CR+PR using RECIST 1.1). These analyses are exploratory in nature and no adjustment for multiple comparisons will be made.

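### Minor, exploratory only: the named paired t test has about 77% power at 20 pairs, not the stated 80%, and the ETV1 protein change is tested against response only as three categories with no stated cut-off

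*Combined protocol and SAP*

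**What the plan says.** Section 14.0 (Biostatistics, exploratory studies) plans mandatory paired biopsies in 20 phase II patients, with further biopsies optional if funding is found. It justifies the number thus: "This sample size provides 80% power to detect a standardized difference of 0.55 assuming 2 sided one sample paired t test", at the 10% level, and adds: "The variable of interest will be change in protein levels".

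A numbered list of seven analyses follows.

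- Item 1 concerns "ETV1 protein level by western blot (WB) as a continuous variable". The before/after change "will be recorded as up, down, and no-change (categorical response"), and is then tabulated with percentages. The only test named is against response: "It will be correlated with response using the Fisher's exact test".
- Item 2 concerns the ETV1-dependent gene signature. It forms a continuous composite score from the expression change, which "will be correlated with clinical response using the Wilcoxon rank test".

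The closing paragraph says that before/after changes, including protein measurements, are of interest and will be related to RECIST response. It continues: "These analyses are exploratory in nature and no adjustment for multiple comparisons will be made".

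Section 10.2.2 has excused patients replaced until 20 pairs are obtained and makes later biopsies optional. Section 2.0 calls 20 a minimum.

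**The concern.** There are two small points.

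First, the power sentence contains every input needed to check it, and the named test does not give the stated figure. The power statement is the plan's only statistical justification for the number of mandatory research biopsies, so it should be right for the test it names.

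Second, item 1 declares a continuous measurement and then tests only a three-way label derived from it. Two patients whose ETV1 protein fell by very different amounts count the same once both are labelled down. The boundary of no-change is not given in Section 2.0 (correlative objective), Section 10.2.5 (item 1d) or Section 14.0. With 20 patients, moving that boundary can move several of them between columns of the table. A boundary chosen after the response data are known would make the Fisher p-value hard to interpret.

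At stake is the clarity of one exploratory analysis and the accuracy of one planning figure.

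**Working it through.** **1. Power of the paired comparison**

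Inputs, all from Section 14.0: n = 20 pairs; standardized difference d = 0.55, read as mean paired change divided by the SD of the paired change; two-sided one-sample (paired) t test; alpha = 0.10.

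*Reproducing the stated 80%.* Normal approximation:

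- d × √n = 0.55 × √20 = 2.460
- power = Φ(2.460 − 1.645) = Φ(0.815) = 79.2%
- n for 80% = ((1.645 + 0.842) / 0.55)² = 20.4

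This is close to the stated figure and is its likely source.

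*The test the sentence names.* Noncentral t with 19 degrees of freedom, noncentrality 2.460, critical value 1.729:

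- power at 20 pairs = 76.6% (a simulation of 400,000 trials gives 76.5%)
- 21 pairs: 78.5%; 22 pairs: 80.2%
- standardized difference giving 80% at 20 pairs: 0.577

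*Other readings do not rescue the figure.* A one-sided t test at 10% gives 86.9%, and a two-sided t test at 5% gives 64.6%.

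The overstatement is 80 − 76.6 = 3.4 percentage points.

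**2. The ETV1 analysis**

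| | Item 1 (ETV1 protein) | Item 2 (ETV1-dependent genes) |
|---|---|---|
| Declared type | continuous | continuous |
| Form tested against response | up / down / no-change | continuous score |
| Test | Fisher's exact | Wilcoxon rank |
| Cut-off needed | yes | no |
| Cut-off given | no | not applicable |

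The plan thus already uses, for the companion ETV1 readout, a test that keeps the size of the change and needs no cut-off.

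**3. Does the categorical coding lose power?**

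The documents give neither a distribution for the ETV1 change nor a size for its association with response, so every input here is an assumption. Common setting: 20 patients with 11 responders and 9 non-responders (55%, midway between the plan's 45% and 65%), two-sided 10% level, exact p-values.

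*Normal change, responders shifted from non-responders, no-change band ±0.5 SD:*

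| Shift | Average fall in ETV1 | Wilcoxon | Fisher, three categories |
|---|---|---|---|
| 0.4 SD | 0.55 SD | 21% | 16% |
| 1.2 SD | 0 SD | 79% | 62% |
| 1.2 SD | 0.55 SD | 79% | 62% |
| 1.2 SD | 1.0 SD | 79% | 54% |
| 1.2 SD | 1.5 SD | 79% | 42% |
| 2.0 SD | 0.55 SD | 99% | 95% |

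*Switch-like change: ETV1 either falls by 1.5 units or does not, noise SD 0.3, band ±0.75:*

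| Falls in responders / non-responders | Wilcoxon | Fisher, three categories |
|---|---|---|
| 80% / 20% | 77% | 84% |
| 90% / 30% | 76% | 84% |
| 80% / 30% | 61% | 66% |

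Under a normal shift the Wilcoxon test is ahead, by anything from about 4 to 37 points in these rows. Under a switch-like change Fisher's test is ahead by 5 to 8 points. The ranking turns on a distribution that nobody yet knows.

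**The case against.** The strongest reply on the power figure is that 80% is a fair rounding of the usual normal approximation, that 20 is a floor, and that two optional pairs would close the gap. The first part explains the figure, but the sentence names a t test, and with 19 degrees of freedom the two methods differ by 2.6 points (79.2 − 76.6). The second part is true but not something to plan on, since Section 10.2.2 ties later biopsies to additional funding.

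On ETV1, Section 10.2.5 describes the protein as very unstable (item 1c) and says that no antibody suitable for IHC exists (item 1d). Coarse coding of such a readout is defensible, and item 2 already supplies a continuous analysis of ETV1 activity against response. This stands as a reason to keep the categorical table. It does not supply the missing cut-off, and it is no reason to omit the continuous analysis of a variable that the plan itself calls continuous.

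Two stronger readings are tempting, and the documents do not support them.

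- *That the t test is left unattached because no item repeats it or names a protein.* The test, sidedness, level and variable stand just before the list, and the closing paragraph says that before/after changes in protein measurements are of interest. For exploratory work, naming one protein would be added detail, not a correction.
- *That ETV1 protein is the trial's main pharmacodynamic marker.* The documents list it among many correlates and give it no such rank.

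**Conclusion.** The point holds as a minor one. The named t test has about 77% power at 20 pairs and a standardized difference of 0.55, against the stated 80%. That result rests only on the plan's own inputs and on reading the standardized difference as the mean paired change over its SD.

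Item 1 tests a continuous ETV1 change only as a three-way category with no stated cut-off. The Fisher test remains valid; what is lost is the size of the change and protection against a cut-off chosen after the fact.

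A reader might infer from the 1.2 SD rows that Fisher's test gives up 15 points of power or more. That does not follow: the figure depends on an assumed normal shift of one size, shrinks to about 4 or 5 points at 0.4 or 2.0 SD (band ±0.5 SD, average fall 0.55 SD), and reverses for switch-like changes. No fixed loss should be claimed.

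These analyses are exploratory and unadjusted. The primary endpoint and its decision rule are unaffected.

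**What to change.** In Section 14.0:

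1. Replace the power statement with: *20 pairs give about 77% power for a standardized difference of 0.55 (80% for 0.58), two-sided paired t test, alpha 0.10.*
2. In item 1, also relate the continuous ETV1 change to response with the Wilcoxon rank test, as item 2 does for its score.
3. Keep the up/down/no-change table and its Fisher test if wanted, but state the no-change cut-off before any response data are examined.

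The cost is a few sentences and a slightly less favourable power figure. No extra patients, biopsies or assays are needed, and the primary analysis does not change.
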